3. ICICLLE TRIAL DESIGN

IcICLLe Study (initial phase)

A feasibility study to investigate i) the mechanism of action of ibrutinib and ii) the biological response to ibrutinib in two separate cohorts of patients; (A) treatment naïve and (B)i relapsed/refractory CLL.

There will be 20 patients in each cohort; therefore a total of 40 patients will initially be recruited.. All patients will receive continuous oral therapy with ibrutinib (420 mg OD) from registration until disease progression.

We will test the patterns of response to ibrutinib in both the treatment naïve and the relapsed/refractory patient cohorts.

IcICLLe Extension Study

The *IcICLLe extension study* will investigate if ibrutinib combined with obinutuzumab can increase the number of patients achieving MRD negativity in peripheral blood and bone marrow.

Two cohorts of patients will be evaluated; cohort (B)ii ibrutinib naïve relapsed/refractory CLL patients, and cohort (B)iii patients initially enrolled on the IcICLLe trial as relapsed/refractory patients and treated with at least 6 months of ibrutinib therapy (i.e. previously in cohort (B)i).

Please note that treatment naïve patients enrolled on IcICLLe in the initial phase—cohort (A)—will not be eligible to take part in the IcICLLe Extension Study and thus will continue with ibrutinib monotherapy.

In the IcICLLe extension study, ibrutinib and obinutuzumab will be administered in combination. Ibrutinib will be given as continuous oral therapy (420 mg OD) from registration until disease progression. **The ibrutinib naïve cohort in the IcICLLe extension study should receive ibrutinib 24 hours before the obinutuzumab (Day 0) to help reduce potential infusion reactions.** Obinutuzumab will be given intravenously at a dose of 1000 mg on days 1, 8, and 15 of cycle 1 and on day 1 of cycles 2- 6 (see section 7.1 for further information of obinutuzumab scheduling)

We will test the patterns of response to ibrutinib and obinutuzumab in both the ibrutinib-naïve and ibrutinib-treated relapsed/refractory patient cohorts.

By studying this and deriving the mechanism of action in both treatment arms we hope to ascertain the most appropriate drugs to combine with ibrutinib and inform how this might be done. This will help to define if this is an appropriate drug to use in combination and/or to take forward into randomised Phase II/III trials of ibrutinib in CLL.

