- Adequate renal function, defined as estimated creatinine clearance $\geq 30 \text{ mL/min}$ using the Cockcroft-Gault equation
- Minimum platelet count of $\geq 50 \times 10^9/\text{L}$
- Absolute neutrophil count $\geq 1.0 \times 10^9/\text{L}$ (unless due to direct marrow infiltration by CLL (to be confirmed via bone marrow biopsy))

Cohort (B)iii: Ibrutinib treated patients (extension phase only – up to 20 patients)

Patients enrolled on the IcICLLe trial as relapsed/refractory patients who have received treatment with Ibrutinib on the IcICLLe trial for at least 6 months

¹² If there are known to be any atypical features, please send a peripheral blood to HMDS for evaluation at least two weeks prior to the screening bone marrow sample.

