- History of severe allergic or anaphylactic reactions to humanised or murine monoclonal antibodies. Known sensitivity or allergy to murine products.
- Vaccination with a live vaccine a minimum of 28 days prior to registration.
- Patients with Progressive Multifocal Leukoencephalopathy (PML).
- No known allergy to obinutuzumab or excipients

Cohort (B)i and(B)ii: Relapsed/refractory (initial phase – 20 patients, extension phase 20-40 patients)

- Previous treatment with ibrutinib or an alternative inhibitor of B-Cell receptor pathway

In terms of exclusion criteria; patients currently participating in IcICLLe and wishing to consent for the IcICLLe extension study must not contravene any of the exclusion criteria above.

Please note that treatment naïve patients enrolled on IcICLLe will not be eligible to take part in the IcICLLe Extension Study.

¹³ Patients may be considered eligible if an active infection is being treated with a short course of antibiotics during the screening period. However, a patient cannot be registered and treated on the trial until the active infection has resolved and the antibiotics have stopped.

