7.2.3.1 MRD negative remission stopping rules

MRD will be measured in the peripheral blood and bone marrow at the time-points described in section 7.2.3 above. The MRD negative confirmation date is defined as the date of the first MRD negative peripheral blood (PB) sample. MRD negative status must be confirmed by subsequent PB and bone marrow (BM) assessment within 6 months of the first MRD negative sample.

Patients receiving treatment on IcICLLe who become MRD negative will stop therapy as described below. MRD monitoring will continue according to the trial visit schedule.

Patients receiving ibrutinib + obinutuzumab

- If PB is MRD negative **during** the 6 cycles of obinutuzumab treatment, and MRD negative remission is confirmed by PB and BM assessment, the participant will receive 12 months further ibrutinib from the end of obinutuzumab treatment. If the patient remains MRD negative after these 12 months of further treatment, ibrutinib will be stopped.
- If PB is MRD negative **after** the 6 cycles of obinutuzumab, and MRD negative remission is confirmed by PB and BM assessment, patients will receive further ibrutinib treatment to double the duration of ibrutinib treatment¹⁵ from the first MRD negative PB sample. If the patient is still MRD negative at the end of this extra treatment time, ibrutinib will be stopped.
For example:
 - If the patient has their first MRD negative blood sample at 9 months, the patient will receive 9 months further ibrutinib treatment: 18 months in total.

Patients receiving ibrutinib monotherapy

- If PB is MRD negative after 12-18 months of ibrutinib treatment, and MRD negative remission is confirmed by PB and BM assessment, patients will receive further ibrutinib to double the duration of treatment from start of ibrutinib to the first MRD negative sample. If the patient remains MRD negative in the PB after this period of treatment, ibrutinib will be stopped.
For example:
 - If the patient has their first MRD negative blood sample at 12 months, the patient will receive 12 months further ibrutinib treatment: 24 months in total.
 - If the patient is confirmed MRD negative with a BM at 15 months, the patient will receive 15 months further ibrutinib treatment: 30 months in total.

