7.10 Patient Follow Up

All patients will remain on study treatment for at least 12 months unless their disease progresses or the patient achieves clinical complete remission or MRD-negative remission according to the modified IWCLL Response Criteria. Guidance for patients achieving an MRD-negative remission is given in Section 7.2.3.

After they have received ibrutinib treatment for a minimum of 6 months, patients in the relapsed/refractory IcICLLe cohort (B(i)) may be given the option to continue treatment via the IcICLLe extension study.

Patients in the treatment naïve cohort of IcICLLe who have stable disease or have maintained a response will remain on ibrutinib treatment, with the cost of ibrutinib paid for by collaborating pharmaceutical company, until disease progression or confirmed MRD negative remission.

All patients will be followed up for trial outcome measures until death.

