12. STATISTICAL CONSIDERATIONS

12.1 Definition of Outcome Measures

12.1.1 Primary Objectives / Outcome Measures

- Proportion of patients achieving MRD-negative remission by IWCLL criteria (depletion of CLL below 0.01% in the peripheral blood and bone marrow) in a) the initial phase of the study at or before the 6 month assessment and b) the Extension Study at or before the 9 month assessment. Independent decisions will be made for each study (initial and extension).

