12.2.2 IcICLE Extension Study

The primary endpoint is the dichotomous variable, MRD Negativity. The precise specification for determining whether a patient is MRD-negative is detailed in section 7.2.3.

We will judge the rate of activity of the experimental regimen using this outcome measure. Under Ibrutinib alone, we would expect a negligible proportion of patients to become MRD-negative. We will regard the combined regimen as worthy of further clinical investigation in a larger, randomised trial if we find reasonable evidence that the rate of activity exceeds 20%.

We will analyse the activity rate of MRD Negativity using a Bayesian method. With binomial data, we can express our prior beliefs on activity using a Beta distribution and use the conjugacy property to express our posterior beliefs as another Beta distribution.

The experimental regimen has not been investigated before so we have no strong prior information. As such, we will use a weakly-informative prior. This is achieved using a Beta(1, 1) distribution, equivalent to saying a-priori that we consider no activity rate to be any more or less likely than any other. After n patients have completed treatment, r of whom become MRD-negative, our posterior beliefs about the activity rate will be described by a Beta(1+r, 1+n-r) distribution. At the end of the trial, we will declare the regimen as showing sufficient activity to warrant further investigation if we are at least 50% confident that the level of activity exceeds 20%. We refer to this as the activity decision rule.

It is possible but not expected that fewer than 40 patients will actually register to this study. For instance, there might be unanticipated and unavoidable shortfalls in recruitment. A benefit of using the Bayesian method is that we will be able to handle deviations from target recruitment in a consistent manner by invoking the Bayesian decision rule described above on the available data.

For all trial sizes between 30 and 40 patients inclusive, the activity decision rule has the following operating characteristics:

- If the true activity rate is 30%, the probability of approving the regimen is always greater than 90%;
- If the true activity rate is 10%, the probability of approving the regimen is always less than 10%;
- The rule never approves the regimen when observing responses in fewer than 18.7% of patients.

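### Cohort (B)iii patients need not be MRD-positive at extension entry, so negativity reached on ibrutinib alone could be credited to the combination in the pooled activity decision

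*Protocol*

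**What the plan says.** **Entry.** The only criterion specific to (B)iii in Protocol 4.1 is "Patients enrolled on the IcICLLe trial as relapsed/refractory patients who have received treatment with Ibrutinib on the IcICLLe trial for at least 6 months". Section 4.2 adds that rollover patients "must not contravene any of the exclusion criteria above", and no item on that list concerns current MRD status. Section 7.10 opens the option "After they have received ibrutinib treatment for a minimum of 6 months" and names no maximum.

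**Endpoint.** Section 12.1.1 counts MRD-negative remission, below 0.01% in both peripheral blood and bone marrow, for "b) the Extension Study at or before the 9 month assessment". Nothing is said about status at extension baseline.

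**Question.** Section 3 says the extension will investigate "if ibrutinib combined with obinutuzumab can increase the number of patients achieving MRD negativity in peripheral blood and bone marrow".

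**Decision.** Section 12.2.2 applies one Bayesian rule to all extension patients: approve if the posterior probability that the rate exceeds 20% is at least 50%. The prior is flat ("This is achieved using a Beta(1, 1) distribution"). The stated properties cover 30 to 40 patients, and 12.5.2 allows up to 20 of at most 40 to come from (B)iii.

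**Background rate.** Section 12.2.2 states: "Under Ibrutinib alone, we would expect a negligible proportion of patients to become MRD-negative". No figure or time horizon is attached.

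**The concern.** The extension asks what obinutuzumab adds to ibrutinib. Negativity already present before the first obinutuzumab dose says nothing about that. Yet under the written entry criteria and endpoint, a patient who arrives negative in both compartments and stays negative counts as a success of the combination.

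The distortion has one direction: each such patient adds a success and can never add a failure attributable to the regimen. It can arise only in (B)iii, which may supply half of the extension. The decision also turns on a handful of successes (8 of 40), so one or two patients matter.

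**Working it through.** **Inputs from the Protocol:** prior Beta(1,1), 20% threshold and 50% confidence (12.2.2); n from 30 to 40 (12.2.2); (B)iii at most 20 (12.5.2).

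**Assumptions, not in the Protocol:** k patients are already negative in both compartments at entry and remain so, so that each is a certain success. The other n−k patients respond independently with probability 10%.

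**1. Reproduce the plan's figures.** With r successes in n, the posterior is Beta(1+r, 1+n−r).
- P(θ>0.2): 8/40 gives 56.19%, 7/40 gives 40.69%, 7/37 gives 50.03%, 6/35 gives 40.07%. All four match the table in 12.2.2.
- The smallest r that approves is 8 at n=40 and 6 at n=32.
- Over n=30 to 40, P(approve) at a true 10% rate runs from 3.2% to 9.4%, and at a true 30% rate from 90.6% to 95.6%. The lowest approvable proportion is 6/32 = 18.75%. The three stated properties hold.

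**2. Add k already-negative entrants.** With required count r*, P(approve) = P(Bin(n−k, 0.10) ≥ r*−k).

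| k | n=40: needed among the others | P(approve) | Expected overall rate, (k + 0.1(40−k))/40 |
|---|---|---|---|
| 0 | 8 of 40 | 4.2% | 10% |
| 1 | 7 of 39 | 8.9% | 12.25% |
| 2 | 6 of 38 | 17.5% | 14.5% |
| 3 | 5 of 37 | 31.0% | 16.75% |

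At n=32, k=1 requires 5 of 31, and P(approve) goes from 9.4% to 19.3%. Across the 11 sizes from 30 to 40, one such patient takes the figure above 10% at seven: n=30, 31, 32, 34, 35, 36 and 37 (10.6% to 19.3%). At n=40 it takes two.

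**3. Express the unknown as a share.** Let each of 20 (B)iii patients be already negative with probability q, with a 10% rate otherwise and 20 (B)ii patients at 10%. At n=40, P(approve) is:
- q=0: 4.2%
- q=1%: 5.2%
- q=2%: 6.4%
- q=5%: 10.9%
- q=10%: 21.4%

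**4. Effect on a single result.** 8/40 approves at 56.19%. If one of the eight was negative before obinutuzumab and is removed, 7/39 gives 43.7%, and the decision becomes reject.

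**The case against.** **The protocol expects almost none of these patients.** If the proportion negative on ibrutinib alone really is negligible, k is near zero and the effect is small: 5.2% at q=1%, 6.4% at q=2%. This stands as a limit on size. It does not close the gap, because no figure supports the word and time on ibrutinib before rollover is unlimited. A reader might go further and take the monotherapy stopping rules in 7.2.3.1 ("If PB is MRD negative after 12-18 months of ibrutinib treatment, and MRD negative remission is confirmed by PB and BM assessment") as proof that such rollover patients are expected. That is too strong. Those rules also cover cohort (A), which cannot enter the extension, and (B)i patients who decline it. They show only that the event was thought possible.

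**The endpoint is demanding.** It needs both compartments, and 12.2.2 refers to 7.2.3, which asks for three consecutive negative bloods at 3-month intervals and a confirming marrow. So a patient negative in blood alone or marrow alone is not an automatic success, and the affected group is correspondingly small. A patient negative in both at entry can still complete a 6-month confirmation within 9 months.

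**Confirmed negatives are on a path to stopping treatment.** Sections 7.1 and 7.2.3 make their enrolment less natural. These are treatment rules, however, not entry criteria, and they do not reach patients whose negativity is not yet confirmed.

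**The cohorts are also analysed separately (12.3).** An excess confined to (B)iii would be visible, and (B)ii is unaffected. That helps interpretation, but the approve/reject rule in 12.2.2 is pooled.

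**Conclusion.** The gap is real and its effect is conditional. As written, negativity reached on ibrutinib alone could be credited to the combination, and the error could run only towards approval. At n=40 the chance of approving a regimen with a 10% rate in the other patients goes from 4.2% to 8.9%, 17.5% and 31.0% for k=1, 2 and 3; at n=32 one patient takes it from 9.4% to 19.3%. These figures assume that already-negative entrants stay negative; if some do not, the effect is smaller.

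Two stronger conclusions might be drawn and are not supported. The first is that the activity rate is in fact inflated: the Protocol gives no count of such patients. The second is that the stated bound of under 10% is wrong: it is conditional on a true overall rate of 10%, and with k≥1 the expected overall rate exceeds that, so bound and table answer different questions. The defect is one of attribution, not of calculation.

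**What to change.** - In 12.1.1 and 12.2.2 (and the matching text in the synopsis and 2.2), define extension success as conversion from MRD-positive (at least 0.01% in peripheral blood or bone marrow) at the last assessment before extension treatment to MRD-negative in both at or before 9 months.
- Leave any (B)iii patient already negative in both at entry out of both r and n of the activity rule, and report that patient separately. Give the rule's result in (B)ii alone as a sensitivity analysis.
- Reconcile the marrow waiver for rollover patients: the footnote to Schedule B refers to a marrow within 3 months of re-registration, section 5.3.2 to one within 6 months of starting the extension. Until they agree, baseline marrow status is not uniquely defined. This matters only for patients whose baseline blood is negative, since a positive blood result settles the classification.

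**Cost.** No eligibility change is needed and no extra blood sample, because screening blood already goes to the central laboratory. The denominator falls by the few patients excluded, which the rule accommodates between 30 and 40. Starting from 40, removing one, two or three leaves n=39, 38 or 37, where approval at a true 10% rate is 3.7%, 3.2% and 7.1% and at a true 30% rate 93.4%, 92.1% and 95.6%. If exclusions took n below 30, the stated properties would no longer apply and would need to be recalculated.

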4.2 Exclusion Criteria

All patients

- Unwilling to undergo the protocol assessments including the bone marrow examinations
- Active infection (at the time of registration)¹³, history of chronic or recurrent infection
- Other severe, concurrent (particularly cardiac or pulmonary) diseases or mental disorders that could interfere with their ability to participate in the study
- Use of prior investigational agents within 6 weeks
- Pregnancy or lactation
- Unwilling to use appropriate contraception during and for 18 months following treatment
- Central nervous system (CNS) involvement with CLL
- Mantle cell lymphoma
- Known HIV positive
- Patients with active Hepatitis B disease
These patients should not be treated. Hepatitis B virus (HBV) screening should be performed in all patients before initiation of treatment with [Ibrutinib in combination with obinutuzumab]. At a minimum this should include HBsAg-status and HBcAb-status. These can be complemented with other appropriate markers as per local guidelines. Patients with positive serology for Hepatitis B defined as positivity for Hepatitis B surface antigen (HBsAg) or anti Hepatitis B core antibody (anti-HBc) are excluded from the trial
- Active secondary malignancy excluding basal cell carcinoma
- Currently active, clinically significant hepatic impairment Child-Pugh class B or C according to the Child Pugh classification
- Persisting severe pancytopenia (neutrophils $<1.0 \times 10^9/L$) or transfusion dependent anaemia unless due to direct marrow infiltration by CLL (to be confirmed via bone marrow biopsy)
- Active haemolysis (not controlled with Prednisolone at 20 mg or less)
- Patients requiring or who have received anticoagulation treatment with warfarin or vitamin K antagonists within one week of the first dose of ibrutinib
- Patients requiring concomitant use of strong CYP3A4/5 inhibitors (section 7.8.2)
- Patients with evidence or history of transformation and/or PLL
- Major surgery within 4 weeks prior to registration
- Currently active, clinically significant cardiovascular disease, such as uncontrolled arrhythmia or Class 3 or 4 congestive heart failure or a history of myocardial infarction, unstable angina, or acute coronary syndrome within 6 months prior to registration
- History of stroke or intracranial haemorrhage within 6 months prior to registration
- History of severe allergic or anaphylactic reactions to humanised or murine monoclonal antibodies. Known sensitivity or allergy to murine products.
- Vaccination with a live vaccine a minimum of 28 days prior to registration.
- Patients with Progressive Multifocal Leukoencephalopathy (PML).
- No known allergy to obinutuzumab or excipients

Cohort (B)i and(B)ii: Relapsed/refractory (initial phase – 20 patients, extension phase 20-40 patients)

- Previous treatment with ibrutinib or an alternative inhibitor of B-Cell receptor pathway

In terms of exclusion criteria; patients currently participating in IcICLLe and wishing to consent for the IcICLLe extension study must not contravene any of the exclusion criteria above.

Please note that treatment naïve patients enrolled on IcICLLe will not be eligible to take part in the IcICLLe Extension Study.

¹³ Patients may be considered eligible if an active infection is being treated with a short course of antibiotics during the screening period. However, a patient cannot be registered and treated on the trial until the active infection has resolved and the antibiotics have stopped.

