7.4.3 Management of obinutuzumab delays

Treatment with obinutuzumab may be discontinued due to poor tolerability/toxicity at the discretion of the treating physician. For patients with evidence of TLS, drug should be discontinued and the patient treated as clinically indicated. Following complete resolution of TLS complications, the study drug may be re-administered at the full dose during the next infusion in conjunction with prophylactic therapy.

a) Haematological Toxicity

Thrombocytopenia: Special Considerations

- Patients treated with concomitant medication which could possibly worsen thrombocytopenia related events may be at greater risk of bleeding. Patients should be closely monitored for thrombocytopenia, especially during the first cycle; regular laboratory tests should be performed until the event resolves, and dose delays should be considered in case of severe or life-threatening thrombocytopenia.
- Participants who experience G3/4 thrombocytopenia ($<25.0 -50 \times 10^9 /L$) should be closely monitored and transfusion of blood products at the discretion of the treating clinician.

Neutropenia

- For participants who experience G3/4 neutropenia ($<0.5 -1.0 \times 10^9 /L$), we recommend treatment with G-CSF and to delay obinutuzumab until the neutrophils are back above $0.5 \times 10^9 /L$

b) Non-Haematological Toxicity

- If hypersensitivity to obinutuzumab occurs (typically occurring after previous exposure to obinutuzumab), the infusion should be stopped and treatment permanently discontinued. Participants with a known IgE mediated hypersensitivity to obinutuzumab should not be treated.
- Obinutuzumab should not be administered in the presence of a severe infection.
- Prophylactic therapy aimed at preventing a recurrence of a diagnosed infection should be instituted if clinically indicated.

c) Progressive multifocal leukoencephalopathy (PML)

- Cases of PML have been reported in patients treated with anti-CD20 antibodies including obinutuzumab.
- Treatment with obinutuzumab should be withheld during the investigation of potential PML and permanently discontinued in the event of a confirmed diagnosis.

d) Infusion Related Reactions

- If a participant develops hypotension during obinutuzumab IV infusions, the withholding of antihypertensive treatments should be considered at the discretion of the treating clinician for

12 hours prior to and throughout obinutuzumab infusions and for the first hour after administration.

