7.7.1 Prohibited concomitant medications

- Warfarin
- Any chemotherapy, anticancer immunotherapy, corticosteroids (at doses equivalent to prednisone >20 mg per day), experimental therapy, or radiotherapy are prohibited while the patient is receiving ibrutinib treatment.
- Vaccination with live vaccines
- Both ibrutinib and obinutuzumab are contraindicated in patients with clinically significant hypersensitivity to the compound itself or to its excipients
- ACE inhibitors and ARBs

The Sponsor must be notified in advance (or as soon as possible thereafter) of any instances for which prohibited therapies are administered.

Please consult with the CI and Clinical Coordinators via the trials office if unsure about the use of a specific drug.

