7.9.10 Hypersensitivity reactions including anaphylaxis

Anaphylaxis has been reported in patients treated with Gazyvaro. Hypersensitivity may be difficult to distinguish from IRRs. If a hypersensitivity reaction is suspected during infusion (e.g. symptoms typically occurring after previous exposure and very rarely with the first infusion), the infusion must be stopped and treatment permanently discontinued. Patients with known IgE mediated hypersensitivity to obinutuzumab must not be treated.

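### The obinutuzumab allergy item in the exclusion list has its polarity reversed, contradicting the protocol's own treatment sections

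*Protocol*

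**What the plan says.** Under the heading "4.2 Exclusion Criteria", the protocol lists conditions that keep a patient out of the trial. The block for all patients closes with "No known allergy to obinutuzumab or excipients". The exclusion list in the Trial Synopsis carries the same line in the same words.

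Just above it in section 4.2 is a separate allergy item, worded in the usual direction: "History of severe allergic or anaphylactic reactions to humanised or murine monoclonal antibodies". That item also names sensitivity or allergy to murine products. Patients moving from the initial phase to the Extension Study "must not contravene any of the exclusion criteria above". Section 6 says that eligibility is confirmed at registration.

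Three later sections deal with hypersensitivity:

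- Section 7.7.1: "Both ibrutinib and obinutuzumab are contraindicated in patients with clinically significant hypersensitivity to the compound itself or to its excipients".
- Section 7.4.3: "Participants with a known IgE mediated hypersensitivity to obinutuzumab should not be treated".
- Section 7.9.10: "Patients with known IgE mediated hypersensitivity to obinutuzumab must not be treated".

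**The concern.** An exclusion item names the state that disqualifies a patient. Others in the same block do so, for example pregnancy or lactation, or known HIV positivity. The obinutuzumab allergy item instead names the state that the trial presumably wants, so it reads as an inclusion criterion placed in the wrong list.

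Eligibility is an operative rule. A site that follows the line literally cannot register the patients for whom the trial is meant. A site that follows the evident intent departs from the written criterion for each patient it enters. The item concerns safety, and anyone who copies the list into a yes/no check without noticing the negation would carry the wrong answer forward.

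**Working it through.** No figure is involved, so the check is one of logic and of consistency between sections.

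**1. Is the wording genuine and current?** The line stands in the operative text of section 4.2 and again in the Trial Synopsis, identically. It is not part of the amendment log and nothing around it is redacted. The identical wording in two places makes a fault of text extraction an unlikely explanation.

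**2. What does the item do when applied as an exclusion?**

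| Patient | Is the item true of the patient? | Result under this item alone |
|---|---|---|
| No known allergy to obinutuzumab or its excipients | Yes | Excluded |
| Known allergy to either | No | Not excluded |

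Both rows are the reverse of what an allergy exclusion does. Most patients will have no known allergy to this antibody, so the first row covers nearly everyone the trial intends to recruit.

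**3. What do the other sections say about the second row?**

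| Place | Direction | Scope |
|---|---|---|
| 4.2, neighbouring allergy item | Excludes | Severe allergic or anaphylactic reactions to humanised or murine antibodies; sensitivity or allergy to murine products |
| 7.7.1 | Contraindicates | Clinically significant hypersensitivity to ibrutinib or obinutuzumab, or to their excipients |
| 7.4.3 | Bars treatment | Known IgE-mediated hypersensitivity to obinutuzumab |
| 7.9.10 | Bars treatment | Known IgE-mediated hypersensitivity to obinutuzumab |

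All four run against the literal reading of the item.

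**4. What is left uncovered at eligibility?** The neighbouring item is limited to severe or anaphylactic reactions and to murine products. It reaches neither excipient allergy nor a non-severe allergy to obinutuzumab. Sections 7.4.3 and 7.9.10 belong to dose management and precautions and are limited to the IgE-mediated kind. Section 7.7.1 does mention excipients, but it sits in a list of prohibited concomitant medication and is not an eligibility check. So no correctly worded eligibility item covers those two groups.

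**5. Whom does it touch?** The item stands in the block for all patients, so the literal reading affects entry to every cohort. Obinutuzumab is given only in the Extension Study (sections 3 and 7.1), whose total is no more than 40 patients (section 12.5.2). Cohort (A) cannot enter the extension, and cohort (B)i receives ibrutinib alone unless a patient rolls over. The safety consequence is therefore limited to the extension cohorts, (B)ii and (B)iii.

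**The case against.** The strongest reply is that the slip is self-evident. A criterion that would empty the trial cannot be what was meant, and sections 7.4.3, 7.7.1 and 7.9.10 make the intention plain. Misapplication is unlikely, and an allergic patient who did get through registration would still meet those sections before treatment. This stands in part. It limits the practical risk, but it does not make the written rule right, and an eligibility criterion should not depend on the reader reversing it.

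A reader might go further than the documents allow in four ways:

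- **That the protocol as a whole admits allergic patients to obinutuzumab.** It does not. That is true of this item read alone. The neighbouring exclusion and the three treatment sections still stop many of these patients, including those with clinically significant hypersensitivity.
- **That this is the only exclusion naming obinutuzumab.** The hepatitis B item in the same block also names it. What can be said is that this is the only exclusion line that addresses allergy to obinutuzumab by name.
- **That sites are using a wrong checklist.** The eligibility form is not among the documents. An error on it is something to check, not an established fact.
- **That striking out the negation brings the item into line with section 7.7.1.** It would correct the direction only. The result would cover an allergy of any severity, to obinutuzumab alone, whereas section 7.7.1 is limited to clinically significant hypersensitivity and also covers ibrutinib.

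**Conclusion.** The item is wrong as written, in two places, and is inconsistent with three other sections of the same protocol. It is a drafting error in an operative eligibility rule, not a choice of design. It warrants correction because the rule concerns safety and applies at registration.

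Its reach is modest. Literally it touches every cohort; as a safety matter it concerns only the Extension Study, and there mainly patients with excipient allergy or non-severe obinutuzumab allergy, who have no correctly worded exclusion. The MRD endpoint, the sample size, the Bayesian activity rule, the toxicity stopping guidelines and the analyses do not change.

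The conclusion rests on reading the item as the list heading directs, namely that a patient of whom it is true is excluded. It assumes nothing about how sites have applied it.

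**What to change.** Correct the polarity of the item in section 4.2 and in the Trial Synopsis, so that in both places it reads as an exclusion. In the same amendment, the sponsor should reconcile its scope with sections 7.4.3, 7.7.1 and 7.9.10. These differ on how severe or of what kind the hypersensitivity must be, on whether excipients count, and on whether ibrutinib is included. Which scope is clinically right is for the sponsor to decide. Then check that the eligibility form used at registration agrees with the corrected text.

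The cost is a short wording change in two places, a decision on scope, and one check of a form. No design, sample size or analysis work follows.
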